In summary, there is no current effective approach to prevent GDM-related fetal overgrowth. We demonstrated that choline sufficiency was critical for restoring normal placental transport and preventing fetal overgrowth in GDM mice. If similar effects of choline could be validated in humans, the practical impact would be remarkable because currently less than 10% of pregnant women in the U.S. consume the recommended 450 mg/d Adequate Intake of choline (47). Choline is readily available in common foods such as eggs, beans, and meat and is easy and safe to provide via a choline-rich diet or choline supplements. When used in clinical trials, choline supplementation was well tolerated and was not associated with any serious adverse events.

STUDY OBJECTIVES

Specific Aim 1: Determine the effect of MCS during pregnancy on birth weight in GDM.

Specific Aim 2: Determine the influence of MCS on macronutrient transport and epigenetic modifications in the placenta and cord blood.

HYPOTHESIS

Aim 1: We hypothesize that the choline group would have lower birth weight and fewer LGA neonates than the non- choline group.

Aim 2: We hypothesize that the choline group would reduce placental transport and increase DNA methylation of metabolic genes.

STUDY DESIGN

Subjects: A convenient sampling methodology will be adopted. We will recruit pregnant women diagnosed with GDM during the second trimester of pregnancy on a rolling basis. Block randomization will be conducted based on treatment methods (i.e. insulin therapy, oral hypoglycemics, or diet only) to randomly assign participants to the intervention and control groups. Recruitment will be conducted using the following methods: (i) study flyers will be posted

at the prenatal clinic; (ii) the principle investigator and her fellows will identify pregnant women who are potentially eligible by reviewing medical records. All these patients are routinely seen by members of the MFM team fellows. The PI or co-I will introduce the study to potential participants.

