Eligibility Criteria: The inclusion criteria include GDM pregnant women before gestational week 28. GDM is diagnosed with the 2-step process: blood glucose higher than the 140 mg/dL cut-off value after 50 g non-fasting 1-hr and 100 g 3-hr oral glucose challenges. Pregnant women are qualified to participate if they are English- or Spanish- speaking, over 18 years of age, having singleton pregnancy, intending to deliver their babies at Maimonides and are without any of the conditions listed in the exclusion criteria. Exclusion criteria include pre-existing hyperglycemia, diabetes, cardiovascular conditions and liver disease prior to pregnancy. Patients may choose to participate in the study and not donate a biopsy of their placenta or umbilical cord. Patients who desire stem cell donation or storage will not be able to donate a biopsy of their placenta or umbilical cord. These patients will not be excluded from the primary analysis.

Design and Data Collection Procedures:

All interaction with participants will occur at Maimonides while sample analyses will occur at Brooklyn College (where the co-I's lab is located). The PI or co-I will obtain written informed consent from the pregnant women before study entry. Randomization will be done by pharmacy after patient signs consent. It will be block randomization of 10 patients. After randomization, the PI or co-I will provide the participant in the intervention group with choline supplement pills containing 500 mg of choline bitartrate (235 mg choline, Douglas Lab). The participant will consume 2 pills per day to obtain 470 mg choline for 8 weeks. The recommended intake of choline in the form of Adequate Intake (AI) is 450 mg/d for pregnant women and the Tolerable Upper Intake Level (UL) is 3500 mg/d. Since less than 10% pregnant women reach the AI of choline intake and the upper quartile of choline intake is below 900 mg/d (48). The dosage we provide plus the habitual intake of choline in these pregnant women will fall between the AI and UL, i.e. sufficient but not exceeding the limit. The participants in the control group will receive a placebo that contains corn oil. Both groups will also receive standard prenatal multivitamins and 200 mg/d DHA provided by the study group. We will provide the participants with 5 weeks supply of supplements and we will verify their compliance during the time with daily check-off logs of supplement consumption and leftover pill count during their next visit.

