The participants will come in for a total of 3 visits at times of routine clinical care. The first visit will be at 28 weeks of gestation when we enroll the participants, the second visit will be at

32 weeks of gestation, and the third visit will be at 36 weeks. There are additional routine clinic visits (e.g., at 32 weeks) during which information can be obtained if a patient missed a study visit. We will collect a baseline questionnaire at the first visit (approximately 20 minutes), conduct 3-day dietary recalls after the first visit (approximately 20 minutes, each), and check current weight and collect 20 mL blood samples at all visits. At delivery, we will collect placenta samples and cord blood from the participants (**Figure 3**).

Baseline questionnaire: The questionnaire includes demographic and medical information such as age, due date, ethnicity, parity, marital status, education level, occupation, household income, medical insurance, substance use, medication use, nutrition supplement, family history of chronic diseases, and self-reported pre-pregnancy weight.

[figure not shown]

Figure 3. Study design

Dietary assessment: Three 24-hr dietary recalls, 2 on weekdays and 1 on a weekend day, will be obtained from each participant by a trained research assistant (RA) via phone calls following the first visits to quantify dietary choline intakes. The multi-pass method of Harnack and colleagues will be used (49). This method is widely used in dietary recall data collection for research (e.g. National Health and Nutrition Examination Survey) and **validated for its accuracy in assessing dietary intake (50)**. The RA will record food identification, quantity, ingredient specification, preparation method and enter data into the Nutrition Data System for Research (NDSR) software to analyze choline intake. The RA will also ask participants about their **physical activity (PA)** during the past 24 hours using the PA recall instrument (51).

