Anthropometric measurements and blood collection: We will measure the participants' weight and height using a medical weighing scale with mechanical height rods during the visits. To minimize food-related concentration differences in plasma biomarkers, participants will be instructed not to consume food for at least 4 hours before their blood draw in the morning. This is a standard recommendation for prenatal visits and is considered as safe (52, 53). We will also have preventative measures such as an examination bed to rest in and juices, food, and water should the women need them. About 20 mL of fasting venous blood will be drawn from each participant during the visits by a fellow/resident/nurse. Blood samples will be collected into one EDTA blood collection tube and one serum separator tube and centrifuged to obtain plasma, buffy coat, and serum. Samples will be processed and stored at -80°C at Brooklyn College until being used for analytical measurements.

Blood glucose management: We will obtain information about fasting glucose, hemoglobin A1C, medication and insulin therapy from medical charts of the participants.

Birth information and sample collection at delivery: The participants will notify the PI or co-I when they are admitted to the birth center by phone. We will also send them reminders as their due dates are approaching. In addition, **the birth center medical staff will be given a list of participant names, thus they will also contact the PI or co-I if a participant checks in when none of the study staff is on site.** The research team will be available 24/7. Once the baby is delivered, we will collect two tubes of cord blood to retrieve serum, plasma, and buffy coat. We will measure the size and weight of the placenta and process the placenta using the following method: full-thickness placental biopsies will be obtained using a 6-mm Keyes punch and stabilized in RNeasy[®] (for RNA), or frozen in liquid nitrogen (for other purposes). Samples will be transported to the co-I's lab for long-term storage at -80C before use.

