Data Analysis: *Specific Aim 1: Determine the effect of maternal choline supplementation (MCS) during pregnancy on birth weight in GDM.* To achieve this aim, we will compare the birth weight as well as incidence of LGA between the intervention versus control group. We will also assess the influence of MCS on blood and placenta choline metabolite status, as well as the correlation between total choline intake (diet + supplement) or choline metabolite status and birth weight.

Dietary intake assessment: As mentioned above, dietary intake data collected from 3-day dietary recalls will be analyzed by the NDSR software (54, 55). Daily intakes of total choline will be calculated by multiplying the frequency of consumption by the sum of choline derivatives including free choline, phosphatidylcholine (PC), glycerophosphocholine (GPC), phosphocholine, and sphingomyelin of each food item(56). Daily intakes of betaine (the oxidation product of choline) will be calculated by multiplying consumption frequency and

betaine content of each food. Average daily intakes will be calculated as the average daily consumption of total choline and betaine over the 3 days of dietary recalls.

Measurements of choline metabolites: Free choline, betaine and other choline derivatives [e.g. PC, GPC, lysophosphatidylcholine, dimethylglycine, trimethylamine oxide (TMAO)] will be measured in maternal plasma using liquid chromatography (LC)-mass spectrometry (MS) /MS (57, 58) as was conducted in previous studies. **To ensure the accuracy and reproducibility of data**, stable isotope labeled standards will be used in extraction, all samples will be quantified based on a 6-point standard curve, and each sample will be run in duplicate. Samples with a coefficient of variation (CV) % higher than 5% within run or 10% between run will be rerun.

Specific Aim 2: Determine the influence of MCS on macronutrient transport and epigenetic modifications in the placenta and cord blood. To achieve this aim, we will determine expression of fat and glucose transporters, as well as the upstream regulating pathways AKT/mTOR in placental biopsies from the participants. We will measure the site-specific DNA methylation of key growth and metabolism related genes in the placenta and cord blood.

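### The planned correlation of total choline intake with birth weight specifies no adjustment for energy intake or maternal size, so self-selected diet can attenuate the hypothesised negative association

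*Combined protocol and SAP*

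**What the plan says.** All references are to the combined protocol and SAP.

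- **Data Analysis, Specific Aim 1.** After the comparison of groups on birth weight and LGA, the plan adds the "correlation between total choline intake (diet + supplement) or choline metabolite status and birth weight". No coefficient, model, covariate or treatment of arm is given. No covariate adjustment is specified anywhere else in the document.
- **Dietary intake assessment.** Intake is absolute: "Average daily intakes will be calculated as the average daily consumption of total choline and betaine over the 3 days of dietary recalls". No energy-adjusted intake is defined.
- **Dietary assessment.** Staff will "enter data into the Nutrition Data System for Research (NDSR) software to analyze choline intake". Energy is not mentioned as an output.
- **Design and Data Collection Procedures.** The supplement part of total intake is assigned: "The participant will consume 2 pills per day to obtain 470 mg choline for 8 weeks". The control group receives placebo.
- **Maternal size.** The baseline questionnaire covers "family history of chronic diseases, and self-reported pre-pregnancy weight", and staff measure "weight and height using a medical weighing scale with mechanical height rods during the visits". No analysis is tied to either.
- **Hypothesis, Aim 1.** "We hypothesize that the choline group would have lower birth weight and fewer LGA neonates" This is a between-group statement; a negative correlation with intake is its implied counterpart.

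**The concern.** Total intake adds a randomised quantity to a self-selected one. Dietary choline comes from ordinary foods, so in absolute milligrams it should be higher in women who eat more, and larger women may well eat more. Food intake and maternal size are both plausible determinants of birth weight. Randomisation is blocked on GDM treatment method. It balances the arms on average, but it cannot balance women across levels of dietary choline, so analysing within arms does not remove the problem.

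Bias by this route would be positive, opposite to the hypothesised direction. The correlation of intake or status with birth weight is the plan's only stated dose-response evidence. A null or weakly positive result on intake could be read as contradicting the randomised result when it reflects only how much the women eat.

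**Working it through.** **Inputs from the document.** Supplement 470 mg/d or none, allocation 1:1; 30 per group with 10% dropout; alpha 0.05 (two-sided assumed). The stated dropout arithmetic reproduces: 30 × 0.9 = 27 per group, 54 in total. The plan gives no figure for the correlation analysis, so there is none to reproduce.

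**Assumed inputs, not in the document.** Correlation of choline with energy 0.5 to 0.7; of energy with birth weight 0.2 to 0.3; SD of dietary choline 100 to 200 mg/d. On spread, the document says only that "less than 10% pregnant women reach the AI of choline intake and the upper quartile of choline intake is below 900 mg/d", which does not fix an SD.

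**Step 1: dietary choline, arm adjusted, no true effect.** Spurious r = r(choline, energy) × r(energy, birth weight), from 0.5 × 0.2 = 0.10 to 0.7 × 0.3 = 0.21. By Fisher z with arm partialled out, the SE is 1/√(54 − 4) = 0.141. The shift is atanh(0.10)/0.141 = 0.71 to atanh(0.21)/0.141 = 1.51, and the two-sided rejection probability is 11% to 33%. With each arm analysed separately (n=27), it is about 8% to 18%.

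**Step 2: total intake, arms pooled, no true effect.** A 0/470 split at 1:1 has SD 470/2 = 235 and variance 55,225. The spurious r shrinks by the factor √(diet variance / total variance). Here the SE is 1/√51.

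| Dietary SD (mg/d) | Total variance | Share from supplement | Factor | Spurious r | Rejection |
|---|---|---|---|---|---|
| 100 | 65,225 | 85% | 0.39 | 0.039 to 0.082 | 6% to 9% |
| 150 | 77,725 | 71% | 0.54 | 0.054 to 0.113 | 7% to 13% |
| 200 | 95,225 | 58% | 0.65 | 0.065 to 0.136 | 7.5% to 16.5% |

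**Step 3: masking of a true effect, arms pooled.** Further assumptions: birth-weight SD 500 g, dietary SD 150 mg/d, and one confounder correlated 0.6 with diet and 0.3 with birth weight. Adjusted here means total intake with the confounder partialled out. At N = 54, significance needs |r| above 0.27. Detection rates come from 4,000 simulations.

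| True effect per 470 mg/d | r unadjusted | r adjusted | Significant negative, unadjusted | Significant negative, adjusted |
|---|---|---|---|---|
| 100 g | −0.02 | −0.12 | 4% | 13% |
| 200 g | −0.14 | −0.23 | 17% | 39% |
| 350 g | −0.31 | −0.38 | 63% | 83% |
| 700 g | −0.59 | −0.64 | about 100% | about 100% |

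**Step 4: when the sign reverses.** Pooled, the unadjusted correlation is zero at a true effect of 470 × 0.6 × 0.3 × 150 × 500 / 77,725 = 82 g. With dietary SD 100 to 200 mg/d and confounder correlations of 0.4 to 0.7 (diet) and 0.2 to 0.4 (birth weight), this point runs from 29 to 138 g. Within one arm, where only diet varies, it is 470 × 0.6 × 0.3 × 500 / 150 = 282 g, with a range of 94 to 658 g.

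**The case against.** The strongest reply is that the planned exposure includes a randomised 470 mg/d, which appetite and body size cannot drive. Under the assumed spreads it supplies 58% to 85% of the variance in total intake. This stands, and it limits the point in two ways. A reader might infer that confounding will produce a positive correlation that hides the negative one; with arms pooled, that holds only for small true effects. A reader might also apply the 11% to 33% false-rejection range to the planned analysis, but it belongs to dietary choline with arm adjusted, which the plan does not describe. The plan is also sized for a birth-weight difference above 20%. At 700 g (20% of an assumed 3,500 g mean), adjustment makes no practical difference to detection.

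A second reply concerns metabolite status. It is tempting to extend the upward bias to it, but nothing in the documents shows that plasma choline metabolites rise with energy intake or body size. The plan also asks for at least four hours without food before blood draws, to limit food-related variation. This stands.

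Third, the document is silent on adjustment; it does not exclude it. That is correct, and the point is that adjustment is unspecified. A plain correlation is nevertheless what the wording describes.

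Finally, this is a supporting analysis. That too stands: the randomised comparison does not depend on it.

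**Conclusion.** The point holds for the dietary component of choline intake and is minor. Run as worded, the correlation mixes self-selected diet with food intake and maternal size, with an expected upward bias. With arms pooled, the consequence is mainly attenuation, material for true effects of about 100 to 350 g, together with modest inflation of false rejection. The larger distortion is confined to dietary choline analysed with arm adjusted or within an arm.

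Every size given rests on assumed correlations and SDs. The calculations treat a single confounder as measured without error; three recalls and a self-reported weight would leave some confounding after adjustment. The documents do not support a claim about the direction of bias for metabolite status, or any claim that the comparison of birth weight and LGA between arms is biased.

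**What to change.** In Data Analysis, Specific Aim 1, replace the plain correlation with a pre-specified linear regression of birth weight on:

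- randomised arm;
- energy-adjusted dietary choline (residual method, or dietary choline with energy as a covariate);
- pre-pregnancy BMI, from the self-reported weight and measured height.

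Report the arm and dietary coefficients separately, with confidence intervals. Include arm and BMI in the metabolite model as a precaution. Label the dietary and metabolite associations non-randomised and exploratory.

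The cost is analysis wording and about three degrees of freedom. Weight, height and recalls are already collected; total energy is assumed to be obtainable from the recall entries, and the plan should say so. The dietary coefficient will be imprecise: at N = 54, 80% power needs |r| of about 0.37, whereas in the central case a 200 g effect per 470 mg/d gives an adjusted within-arm correlation of only about −0.11. Adjustment makes that estimate less biased but leaves it imprecise, so a null dietary result should not be read as evidence against choline.

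### The written formula for choline and betaine intake has no amount term and conflicts with the 24-hour recalls; the basis of the 235 mg pill content is also not stated

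*Combined protocol and SAP*

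**What the plan says.** **Instrument.** The Dietary assessment paragraph (under Design and Data Collection Procedures) specifies: "Three 24-hr dietary recalls, 2 on weekdays and 1 on a weekend day, will be obtained from each participant". For each recall, "The RA will record food identification, quantity, ingredient specification, preparation method and enter data" into NDSR to obtain choline intake.

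**Calculation.** In the Data Analysis section, the Dietary intake assessment paragraph first says that "dietary intake data collected from 3-day dietary recalls will be analyzed by the NDSR software". It then gives the rule: "Daily intakes of total choline will be calculated by multiplying the frequency of consumption by the sum of choline derivatives" for each food item. The betaine rule has the same form: "Daily intakes of betaine (the oxidation product of choline) will be calculated by multiplying consumption frequency and" the betaine content of each food. Daily values are averaged over the three recall days.

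**Supplement.** Design and Data Collection Procedures describes pills of "500 mg of choline bitartrate (235 mg choline"), two a day, for a stated 470 mg of choline. Compliance is checked with "daily check-off logs of supplement consumption and leftover pill count during their next visit".

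**Use.** Under Specific Aim 1, total choline intake, meaning diet plus supplement, is to be correlated with birth weight. This is in addition to the between-arm comparison of birth weight and LGA. The plan gives no formula for the supplement part of that total.

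**The concern.** The only formula written down for dietary choline multiplies how often a food was eaten by what the food contains. That form suits an instrument that asks about frequency. This trial uses recalls, whose main information is how much was eaten, and the formula has no place for it. One of the two references cited for the NDSR step is, by its title in the reference list, a comparison of food frequency questionnaires. This may be where the wording came from, but no such questionnaire is used here.

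The supplement part of the exposure has two gaps. The plan does not say which form of choline the 235 mg refers to, although that figure is to be added to dietary choline and the sum is set against the AI and UL. Nor does it say whether the supplement term is the assigned amount or the amount taken.

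What is at stake is the reported intake and the Aim 1 correlation of total choline intake with birth weight. Two analysts, one following the written formula and one taking the NDSR output, would produce different exposure variables from the same recalls.

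**Working it through.** **1. Diet formula against instrument.**

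Let a food contain *c* mg choline per portion, and let two women each eat it once in the three recalled days, one taking one portion and the other three.

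| | Woman A (1 portion) | Woman B (3 portions) |
|---|---|---|
| Written formula: frequency x content | 1 x *c* = *c* | 1 x *c* = *c* |
| Amount x content | 1 x *c* = *c* | 3 x *c* = 3*c* |
| Three-day mean, written formula | *c*/3 | *c*/3 |
| Three-day mean, amount-based | *c*/3 | *c* |

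Read literally, a true difference of 2*c*/3 mg/d is scored as zero. The documents give no food-level data, so neither *c* nor the spread of portion sizes is available and no overall error can be computed.

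**2. Supplement arithmetic.**

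The plan's own daily figure reproduces: 2 x 235 = 470 mg/d. The stated fraction is 235/500 = 47.0%.

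The molar masses below are calculated from chemical formulas. They are an assumption, not in the documents: choline bitartrate 253.25, choline ion 104.17, choline base (hydroxide) 121.18 g/mol.

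| Meaning of choline | Fraction of salt | Per 500 mg pill | Two pills | Stated 235 mg relative to this |
|---|---|---|---|---|
| Ion | 104.17/253.25 = 41.1% | 205.7 mg | 411.3 mg/d | 14.3% higher |
| Base | 121.18/253.25 = 47.8% | 239.2 mg | 478.5 mg/d | 1.8% lower |

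On the ion basis the daily gap is 470 - 411.3 = 58.7 mg, which is 58.7/470 = 12.5% of the stated amount. On the base basis the stated figure holds to within 2%.

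**3. The AI and UL statement.**

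The plan's statement concerns supplement plus habitual intake, with an AI of 450 and a UL of 3500 mg/d. On the ion basis the AI is reached once habitual intake exceeds 450 - 411.3 = 38.7 mg/d. For an assumed habitual intake of 200 to 900 mg/d, the total is 611 to 1311 mg/d on the ion basis and 670 to 1370 mg/d with the stated 470. Both ranges lie between the AI and the UL.

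**4. Effect of the pill basis on the correlation.**

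An illustrative simulation took 200,000 women split at random between arms, with habitual intake of mean 320 mg/d and SD 80, 120 or 160, and adherence of mean 85% and SD 15 points, cut off at 0 and 100%. All these inputs are assumptions. Total intake computed with 470 mg and with 411 mg correlated at 0.999, 0.998 and 0.998 respectively. Rescaling the pill alone would hardly change the planned correlation. It would change reported intakes and any slope per mg.

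**5. Adherence.**

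If the assigned amount is entered, the supplement term takes two values only, 0 and 470 mg/d. A woman who takes 60% of her pills (an assumed figure) would be entered at 470 rather than 0.60 x 470 = 282 mg/d. The pill counts that would correct this are already collected.

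**The case against.** The strongest reply on the diet side is that portion size is not absent from the plan. Quantity is recorded, the recalls go into NDSR expressly to obtain choline intake, and the analysis paragraph itself opens with NDSR. The frequency sentence may be no more than a loose description of what the software does. A recall also shows how often a food was eaten on the recalled day, so frequency is not meaningless here; only usual, long-run frequency is out of reach. This stands to the extent that a reader may not infer that intake will certainly be computed wrongly, or that quantity will be discarded. It does not remove the conflict, because the one rule written down for the calculation lacks the amount, and it is repeated for betaine.

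On the supplement, a reader might infer that a 500 mg pill does not contain 235 mg choline. The documents do not support that. The figure fails only if choline means the ion, and it fits if choline means the base. The plan does not define the form, and the product documentation is not available to us. A reader might also infer that the choline arm falls below the AI, because 411 is less than 450. That compares the supplement alone with the AI, whereas the plan's statement is about supplement plus habitual intake and survives on either basis.

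The unstated use of pill counts is a gap in specification. No formula for the supplement is given, so there is none to be wrong.

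**Conclusion.** The point holds as a conflict between a stated rule and the instrument it is applied to. The formula for choline and betaine has no amount term, while the recalls record amounts. Taken literally, it would mis-score dietary intake in a named Aim 1 exposure. The size of that error cannot be derived from the documents, and it may not arise if the NDSR output is used.

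The pill content is a matter of undefined basis, with a range of 206 to 239 mg per pill and 411 to 478 mg/d. The range rests on assumed molar masses, and the stated 235 mg lies within it. If the diet data are in terms of choline ion (a further assumption), the supplement is overstated by about 59 mg/d at full adherence.

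The consequences are confined to reported intake and to the correlation of total intake with birth weight. The randomised comparisons of birth weight and LGA do not use this variable, and the statement placing total intake between the AI and the UL is not affected. Nothing here implies a change of dose.

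**What to change.** - **Diet.** Replace the formula in Dietary intake assessment with: daily choline (and, separately, betaine) = sum over all foods in a recall of amount eaten x content per unit amount, as output by NDSR from the recorded quantities, averaged over the three recalls.
- **Pill content.** Reconcile the 500 mg and 235 mg figures against the product's documentation, and state which form of choline the 235 mg refers to. Express supplement and diet choline on the same basis wherever they are added or compared with the AI and UL.
- **Supplement term.** State that it is choline per pill x pills taken per day, from the leftover pill counts, with the daily logs as a check.

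The cost is a few sentences in the plan and one look at the product documentation. Quantities and pill counts are already collected, so no new data are needed. The only side effect may be a restated intake figure.

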Sample Size: We anticipate a 10% dropout rate due to reasons such as participants moving out of the city, pre-term deliveries, or missed placental collection. Therefore, we expect to have at least 27 sets of complete data in each group. A statistical power analysis was performed for sample size estimation accounting for rates of dropout and missing data, based on data from a randomized controlled trial of choline supplementation which demonstrates that 2 x recommended intake of choline for 12 weeks is sufficient to increase plasma choline and alter placental global DNA methylation. The initial sample size of n=30/ group will allow detection of a >20% difference in birth weight, plasma choline and placental DNA methylation at $\alpha < 0.05$ and power = 80%.

Expected Outcomes: The successful completion of this study will provide valuable insights into the use of choline supplement as a modifier of placental macronutrient homeostasis in GDM to improve fetal growth outcomes.

Timetable:

	Quarter 1	Quarter 2	Quarter 3	Quarter 4
Participant Recruitment	n = 20	n = 20	n = 20	
Sample and Data Collection				
Choline measurements		Aim 1	Aim 1	Aim 1
Gene expression and epigenetic measurements		Aim 2	Aim 2	Aim 2
Data analysis				Both Aims
Result dissemination				Both Aims

We expect to complete recruitment by the end of the third quarter and complete dietary record, clinical information, and biosample collection in the middle of the fourth quarter. We will start analytical measurements once we obtain at least a third of the samples. We expect to complete analytical measurements by the end of the year. We will analyze and disseminate data in the last quarter.

Data Safety Committee Team Plans:

Randomization is a block randomization of 5 patients. After every block of randomization, the research team with a pharmacist and at least one external physician outside of the research team [[name]] will analyze the data to ensure that there are no unanticipated adverse effects via ultrasound fetal growth patterns. If unanticipated effects are found, we will report to IRB as per policy.

REFERENCES

1. Ferrara A. Increasing prevalence of gestational diabetes mellitus: a public health perspective. *Diabetes Care*. 2007;30 Suppl 2:S141-6. doi: 10.2337/dc07-s206. PubMed PMID: 17596462.

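### Does counting pre-term delivery as dropout in the sample-size allowance remove those births from the birth-weight comparison?

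*Combined protocol and SAP*

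**What the plan says.** The Sample Size section explains its allowance for loss as follows: "We anticipate a 10% dropout rate due to reasons such as participants moving out of the city, pre-term deliveries, or missed placental collection". It continues: "Therefore, we expect to have at least 27 sets of complete data in each group". The power claim in the same paragraph is attached to the initial 30 per group, which "will allow detection of a >20% difference in birth weight, plasma choline and placental DNA methylation".

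For Aim 1, the Data Analysis section states: "we will compare the birth weight as well as incidence of LGA between the intervention versus control group". It adds a sample-based part to the same aim: "We will also assess the influence of MCS on blood and placenta choline metabolite status". It names no analysis set and gives no rule on gestational age.

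Three other places bear on who is kept:

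- Eligibility Criteria, on women who give no placental or cord biopsy: "These patients will not be excluded from the primary analysis". Pre-term delivery is not among the exclusion criteria.
- Design and Data Collection Procedures, on visits: the second is at 32 weeks "and the third visit will be at 36 weeks". Routine clinic visits are available as a fallback, "during which information can be obtained if a patient missed a study visit".
- Birth information and sample collection at delivery: women and birth-centre staff alert the team to an admission, and samples are taken once the baby is born, at whatever gestational age.

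**The concern.** The list of dropout reasons mixes two kinds of loss. A woman who moves away may take her outcome with her. A woman who delivers early, or whose placenta is not collected, still has a baby whose weight is recorded. One power statement covers birth weight together with plasma and placental measures, so the plan does not visibly separate women without a sample from women without a birth weight.

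If the dropout label were carried into Aim 1, women with a known outcome would be removed because of something that happened after randomisation and that strongly affects that outcome. The groups compared would no longer be the groups randomised. Since no analysis set is named, the choice could also be made with the data in view, in a trial of 30 per group.

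**Working it through.** **Inputs from the plan:** 30 randomised per group, a 10% allowance, 27 complete sets per group, and a target difference above 20%.

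**Assumptions not in the plan:** birth-weight SD 500 g, mean 3,300 g, pre-term rate 5 to 10%, mean weight deficit of a pre-term birth 500 to 1,000 g.

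1. *The plan's own figure.* 30 x (1 - 0.10) = 27 per group, as stated. The allowance is 30 x 0.10 = 3 women per group, shared by at least three named reasons.

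2. *What the allowance counts.* It counts complete sets of data. A woman who delivers before 36 weeks cannot attend the third visit, so her set is incomplete even though her baby's weight is known. The plan itself shows that an incomplete set does not by itself mean removal: missed placental collection is on the dropout list, yet women who donate no biopsy stay in the primary analysis. That retention rule covers non-donation rather than every missed collection, but the principle is visible.

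3. *Shift if pre-term births were left out.* Let p be the pre-term rate and D the mean deficit in each arm. The mean over all births is the mean over term births minus p x D. Leaving pre-term births out therefore moves the group difference by p1 x D1 - p0 x D0. This is zero whenever the two products match. Equal rates and equal deficits are sufficient but not necessary: 0.05 x 1,000 = 0.10 x 500 = 50 g also cancels.

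4. *Size on the plan's own scale.* With the same deficit in both arms, a gap of one birth in 30 gives (1/30) x 500 = 17 g to (1/30) x 1,000 = 33 g.
   - The standard error with 27 per group is 500 x sqrt(2/27) = 136 g, so this is 17/136 = 0.12 to 33/136 = 0.24 of it.
   - The target is 0.20 x 3,300 = 660 g, so this is 17/660 = 3% to 33/660 = 5% of it.
   - A chance gap of this kind is random variation, not bias.

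5. *Wider range.* A 5 to 10 point difference in rate gives 0.05 x 500 = 25 g to 0.10 x 1,000 = 100 g, or 25/136 = 0.18 to 100/136 = 0.73 of the standard error. The upper end needs pre-term birth to use all three allowed losses in one group and none in the other.

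6. *Precision when all births are kept.* SD = sqrt(500^2 + p(1-p)D^2).
   - p = 0.05, D = 500: SD 512 g, and the standard error with 30 per group is 512 x sqrt(2/30) = 132 g.
   - p = 0.10, D = 1,000: SD 583 g, and the standard error is 583 x sqrt(2/30) = 151 g.
   - For comparison, it is 136 g with 27 per group at SD 500 g. Keeping everyone can help or hurt precision slightly. The reason to keep them is comparability of the groups.

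No shift in LGA incidence was computed, because the plan gives no LGA rate to start from.

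**The case for a change.** The best case for a change is that none of the retention statements names pre-term birth. The eligibility statement covers only women without a biopsy. The visit fallback concerns missed visits, and the delivery arrangements show that data can be obtained, not that they will be analysed. Pre-term delivery follows randomisation and bears directly on birth weight, and one sentence naming the analysis set would settle the matter at almost no cost.

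The silence is real, and such a sentence would do no harm. But the objection needs two steps that the documents do not supply. First, someone must turn a sample-size allowance into an exclusion. Nothing tells them to, and the comparison of the two groups carries no restriction. Second, pre-term births must then differ between arms in rate times deficit. The plan gives no reason to expect choline to alter pre-term delivery. Nor does the text say that the power claim was computed on 27: it attaches the claim to 30 per group and says only that dropout was accounted for. What remains is a missing detail whose ordinary default is also the sound choice, namely to analyse every randomised woman with a recorded birth weight in the group to which she was assigned.

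**Conclusion.** The concern does not call for a change. The sentence on dropout is a planning allowance for complete data, its arithmetic is right, and the rest of the plan leans towards keeping pre-term births in the birth-weight and LGA comparison. An analyst who follows the plan as written would keep them and would restrict the complete-sample set to the plasma and placental measures.

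If that default were not followed, a one-birth imbalance would move the estimate by about 17 to 33 g, well inside one standard error of 136 g. The 100 g figure needs an extreme split between the groups. These sizes rest on the assumed SD, mean, pre-term rates and deficits. The reading of the plan does not.
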